9.0 STATISTICAL CONSIDERATIONS

9.1 Sample Size and Study Duration

The proposed randomized Phase 2 study will require enrollment of 90 eligible patients, 45 assigned to each regimen. Enrollment may proceed up to 95 patients to allow up to 5% potentially ineligible patients.

Expected accrual for this study would be similar to the accrual rate of 42 patients/year observed on the ANBL1221 expansion cohort at non-Australian and New Zealand sites as the patient population and eligibility are very similar. We anticipate that given the positive results of ANBL1221 and the reality that this backbone has become widely used for first relapse, there should be similar accrual rates for this trial. Assuming this rate, the trial would take about 2.3 years to complete accrual of up to 95 patients. The study will require an additional 12 months for completion of therapy and toxicity evaluation for a total study duration of approximately 3.3 years.

The sample size may be increased if accrual is fast: specifically, if 30 months after the study commencement the average accrual rate over the previous 3 months is above an annual rate of 41 patients per year, then the study may be amended (blindly to the interim outcome data) and accrual increased to 148 eligible patients. In this case, enrollment may proceed up to 155 patients to allow up to 5% potentially ineligible patients. Assuming an accrual rate of 42 patients/year (this rate would be amended if needed based on observed accrual rate), the trial would take about 3.7 years to complete accrual and a total study duration of ~4.7 years. The amendment would be submitted after the 30-month time point so that the study will not need to be closed to accrual as a result of the increase in the target accrual.

9.2 Study Design

This will be a prospective, randomized phase 2 trial to determine whether the addition of DFMO to the dinutuximab/irinotecan/temozolomide backbone improves the response rate compared to the backbone alone. Patients will be randomized 1:1 to Regimen A (irinotecan/temozolomide/dinutuximab) or Regimen B (DFMO + irinotecan/temozolomide/ dinutuximab), stratified by disease category (measurable vs. evaluable), prior anti-GD2 therapy (prior exposure to anti-GD2 antibody vs. no prior exposure to anti-GD2 antibody), prior DFMO therapy (prior exposure to DFMO vs. no prior exposure to DFMO), and *MYCN* status (amplified vs. non-amplified vs. unknown). We will monitor for differences in the response rate between the two regimens for early indication of futility and efficacy.

9.3 Methods of Analysis

9.3.1 Primary Endpoint

The primary endpoint will be the proportion of eligible patients who are responders. Responders are defined as patients who achieve a minor response (MR) or better, per the revised International Neuroblastoma Response Criteria (INRC),⁶⁸ as their best overall response by the end of 6 cycles as determined by central review. With Amendment 4, patients with a response of MR, PR, or CR that is qualified by “Not Fully Evaluated (NFE)” will be included as responders. See [Section 10.2.3](#) and [Appendix XIV](#) for definition of NFE. Patients with progressive disease (PD) prior to attaining a \geq MR will be considered non-responders. If a patient becomes a responder and later has PD or later goes off protocol therapy, then the patient will be counted as a responder. Eligible patients without any response assessment will be considered non-responders. All eligible patients will be considered evaluable for response. All analyses of response will be conducted as intent-to-treat.

Patients enrolled prior to Amendment 4: Patients will be assessed for response after every 2 cycles for the first 6 cycles, then after every 4 cycles for up to 11

additional cycles. Patients with stable disease or better during the first 4 cycles will be permitted to continue protocol therapy. However, after 6 cycles, patients not demonstrating a response [complete response (CR), partial response (PR), or MR] will be removed from protocol therapy. The decision to remove patients without response after 6 cycles is based on data from ANBL1221, where the majority of responders to I/T/DIN were found to have objective responses after 2 cycles but some patients did not achieve their best response until later cycles. Data including the expanded cohort of patients treated with I/T/DIN on ANBL1221 indicate that 12 of 22 responders (54.5%) experienced their best response after Cycle 2, with the remaining 10 of 22 (45.5%) responders achieving their best response by Cycle 6.³

Patients enrolled on Amendment 4 or later: Patients will be assessed for response after every 2 cycles and may receive a maximum of 6 cycles of protocol therapy. Patients with stable disease or better during the first 4 cycles will be permitted to continue protocol therapy. All patients will go off protocol therapy regardless of response after 6 cycles.

9.3.1.1 Power Calculations

With enrollment of 90 eligible patients (45 to each regimen), this design has 80% power to detect a 20% difference in response rate [40% under the null for Regimen A (as observed on the ANBL1221 including the expanded cohort of patients assigned to the I/T/DIN arm), 60% under the alternative for Regimen B] and type I error of 20%, using a one-sided continuity-corrected test of proportions with pooled variance.

If the study is amended and the sample size is increased to 148 eligible patients (74 on each regimen) due to fast accrual, a 15% difference in response rate will be targeted [40% under the null for Regimen A, 55% under the alternative for Regimen B]. This design has 80% power and type I error of 20%, using a one-sided continuity-corrected test of proportions with pooled variance and interim monitoring for efficacy with a one-sided O'Brien-Fleming rule.

9.3.2 Secondary Endpoints

Progression-free survival (PFS) and overall survival (OS) will be assessed for patients receiving dinutuximab, irinotecan, and temozolomide with and without the addition of DFMO. For PFS, time to event will be calculated from the time of randomization to the occurrence of relapse, progressive disease, or death. For OS, death will be the only event considered and time to death will be calculated from the time of randomization. Patients without a PFS event or death will be censored at the time of last follow-up.

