3.1.5 Timing

Patients must be enrolled before treatment begins. The date protocol therapy is projected to start must be no later than **ten (10)** calendar days after the date of study enrollment. It is strongly recommended that patients do not start treatment on a Friday or weekend. **Patients who are started on protocol therapy on a Phase 2 study prior to study enrollment will be considered ineligible.**

All clinical and laboratory studies to determine eligibility must be performed within 7 days prior to enrollment unless otherwise indicated in the eligibility section below.

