4.1 Overview of Treatment Plan

Patients with high risk neuroblastoma, either primary resistant/refractory or in first relapse or progression, will be randomized to receive one of two arms of therapy: Regimen A consisting of dinutuximab, irinotecan, temozolomide and sargramostim (GM-CSF), or Regimen B, which will include the addition of DFMO to dinutuximab, irinotecan, temozolomide, and GM-CSF. Arms will be balanced with respect to disease category (measurable vs. evaluable), prior anti-GD2 therapy, prior DFMO therapy, and *MYCN* amplification status.

Each cycle of therapy will be 21 days in length, with the exception of Regimen B Cycle 1. Patients randomized to Regimen B will receive a 7-day DFMO pretreatment phase for Days -6 to 0 prior to the start of chemotherapy on Day 1 of Cycle 1 to deplete essential polyamines.

Patients enrolled prior to Amendment 4:

Disease assessments will occur after Cycles 2 and 4. Patients with stable disease or better on disease assessments after Cycles 2 and 4 will continue on protocol therapy. After Cycle 6, patients who achieve a minor response (MR) or better on disease evaluation will continue on protocol therapy. After Cycle 6, patients may remain on study for up to 17 cycles (approximately 1 year of therapy) as long as they maintain a minor response or better on disease assessments performed after every 4th cycle. An end of therapy disease evaluation will be performed after Cycle 17 for patients who complete all planned protocol therapy.

Patients enrolled on Amendment 4 or later:

Disease assessments will occur after Cycles 2 and 4. Patients with stable disease or better on disease assessments after Cycles 2 and 4 will continue on protocol therapy for a maximum of 6 cycles. An end of therapy disease evaluation will be performed after Cycle 6 for patients who complete all planned protocol therapy.

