4.5.5 Additional guidance

- Capillary leak syndrome is an expected side effect of dinutuximab therapy. Complications of capillary leak syndrome can be mitigated if euolemia is maintained. Close monitoring of heart rate and urine output is required, and fluids should be adjusted to compensate for third space losses. The routine use

of diuretics during Days 2-5 is contraindicated unless clinically required (i.e. pulmonary capillary leak with respiratory compromise). Use of furosemide should be avoided when feasible due to ototoxicity concerns.

- Corticosteroid therapy should be used only for life-threatening conditions (i.e. treatment of increased intracranial pressure in patients with CNS tumors, symptomatic bronchospasm, stridor unresponsive to other measures or life-threatening allergic reactions). Corticosteroids will impair the immune activation that is a critical part of the protocol therapy. **The use of steroids at any time during immunotherapy requires clear justification and documentation.**
- The use of IVIG is discouraged. IVIG should not be given within 2 weeks of starting dinutuximab treatment and 1 week after completing dinutuximab therapy.
- Cytokines or growth factors (G-CSF, Interferon, etc.) not included in the Treatment Plan are prohibited during immunotherapy.

4.6 **Regimen B Cycle 1**

4.6.1 Therapy Delivery Map –CYCLE 1 Cycle 1 lasts 4 weeks (28 days). This cycle includes a lead-in of 7 days of DFMO (Days -6 to 0) prior to 21 days of chemotherapy.	Patient COG ID number _____ DOB _____
---	--

Begin Cycle 2 on Day 22 of Cycle 1 or when peripheral counts recover with ANC \geq 750/ μ L and platelets \geq 75,000/ μ L (whichever occurs later). See [Section 5.0](#) for dose modifications. This TDM is on 3 pages.

DRUG	ROUTE	DOSAGE	DAYS	IMPORTANT NOTES
Eflornithine (DFMO) IND# 141913	PO or via NG or Gtube	2250 mg/m ² /dose x 3 doses/day See dosing table in Appendix XII	Days -6 to +7 and Days 15 - 21	Round doses to the nearest 500 mg (see dosing table in Appendix XII). Note: During Days 1-5, consider giving one of the 3 times daily eflornithine doses and temozolomide close together in order to minimize potential for emesis and redosing.

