9.3.4 Assessment of Study Objectives

The primary study aim ([1.1.1](#)) will be assessed by a one-sided continuity-corrected test of proportions with pooled variance to compare the response rates after 6 cycles in the two regimens, and the futility and efficacy monitoring rules ([Section 9.3.3](#)). The response rate by the end of 6 cycles will be calculated on each regimen, including placement of a 95% confidence interval. If a patient is a responder and later has PD or goes off protocol therapy, then the patient will be counted as a responder. If the response rate on Regimen B is significantly better, then it will be considered a therapeutic regimen worthy of further testing in patients with newly-diagnosed high-risk neuroblastoma. In addition, the response rate by the end of 6 cycles (based on confirmed responses) will also be calculated for each regimen, with responders defined as patients who achieve a confirmed minor response or better per the revised INRC⁶⁸ as their best overall response by the end of 6 cycles as determined by central review.

To address secondary objective [1.2.1](#), Kaplan-Meier curves of PFS and OS will be generated by regimen and compared using log-rank tests. PFS and OS will also be evaluated separately in the cohorts of patients enrolled prior to and post-Amendment 4 given the reduction in maximum cycles of therapy from 17 to 6 cycles.

To assess secondary aim [1.2.2](#), toxicities (Grade ≥ 3) experienced on Regimen B will be descriptively summarized.

Exploratory aim [1.3.1](#) will be assessed by exploring the relationship between response (responder vs. non-responder) after 6 cycles on Regimen B with serum cytokine levels (IL1, IL6, TNF-alpha, IFN-gamma, etc.), tumor resident immune cells (NK cells, TAMS, TILS), and critical immune cell suppressing proteins (B7H3, PDL-1) using Fisher's exact test for categorical and Wilcoxon rank-sum test for continuous factors.

To address exploratory objective [1.3.2](#), GD2 levels in tumor cells from bone marrow samples will be correlated with response (responder vs. non-responder) after 6 cycles using Fisher's exact test for categorical and the Wilcoxon rank-sum test for continuous factors.

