15.1 Timing of Imaging

To document tumor, standard CT, MRI, and MIBG (FDG PET/CT or PET/MRI scan if tumor is not MIBG avid) scans must be performed at the following time points:

- within 3 weeks prior to the start of protocol therapy
- end of Cycles 2*, 4 and 6*, then for patients enrolled prior to Amendment 4 every 4th cycle thereafter
- end of therapy*
- at relapse/progression

* Patients with no soft tissue (non-osseous) disease at baseline (i.e., MIBG avid bone lesions or bone marrow involvement only) are only required to undergo appropriate cross-sectional imaging (CT and/or MRI) of primary tumor site at the end of Cycles 2, 6, and end of therapy only. Additionally, CT and/or MRI are required for confirmatory imaging at least 4 weeks after first response is documented for those patients who do not continue on protocol therapy. This is in addition to MIBG (FDG PET/CT or PET/MRI scan if tumor is not MIBG avid) performed at all disease evaluation time points.

Note: Patients with any soft tissue disease (either measurable or non-measurable) at baseline are required to have CT/MRI, and MIBG (FDG PET/CT or PET/MRI scan if tumor is not MIBG avid) scans at all disease evaluation time points.

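### Regimen B's 7-day lead-in puts its scheduled on-treatment disease evaluations about a week later after randomisation, so the raw-date PFS log-rank tilts slightly toward Regimen B

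*Combined protocol and SAP*

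**What the plan says.** **Time origin and censoring.** Section 9.3.2 defines PFS so that "time to event will be calculated from the time of randomization to the occurrence of relapse, progressive disease, or death", and adds: "Patients without a PFS event or death will be censored at the time of last follow-up". Section 10.2.5 repeats the definition.

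**Test.** Under Section 9.3.4, "Kaplan-Meier curves of PFS and OS will be generated by regimen and compared using log-rank tests". PFS and OS are also to be evaluated separately in patients enrolled before and after Amendment 4. No significance level or sidedness is given for the log-rank.

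**Cycle length.** Section 4.1: "Each cycle of therapy will be 21 days in length, with the exception of Regimen B Cycle 1". The Regimen B Cycle 1 delivery map (Section 4.6.1) says "Cycle 1 lasts 4 weeks (28 days" and explains: "This cycle includes a lead-in of 7 days of DFMO (Days -6 to 0) prior to 21 days of chemotherapy".

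**Evaluation timing.** Section 15.1 places imaging within 3 weeks before therapy, then at "end of Cycles 2*, 4 and 6*, then for patients enrolled prior to Amendment 4 every 4th cycle thereafter", at end of therapy, and at relapse or progression. From Amendment 4, therapy stops after Cycle 6 (Sections 4.1 and 9.3.1). Section 7.1 then schedules no routine imaging in follow-up beyond confirming a first response; it records disease status at visits with a window of 2 months either way.

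**Windows common to both arms.** These are the 10-day limit on starting therapy (Section 3.1.5), the 72-hour allowance (Section 4.0), and imaging up to one week before the next cycle (Sections 4.5.2 and 4.7.2).

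**The concern.** Progression that is found on a scheduled evaluation carries the date of that evaluation, not the date on which the tumour grew. If one arm's evaluations come systematically later after randomisation, the same disease course gives longer recorded PFS in that arm, and a log-rank on recorded dates counts the difference as benefit. Here the later arm is the experimental one. The windows shared by both arms blur the gap but do not change its mean.

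The comparison at stake is the PFS part of the first secondary aim (Section 1.2.1), which will be read beside the response result, and the separate look at the pre-Amendment 4 cohort, where the most evaluations are shifted.

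**Working it through.** **1. The plan's own figures.** Regimen B Cycle 1 is 7 + 21 = 28 days, as stated. The 45 per regimen comes from the response endpoint (40% v 60%, one-sided 20%, continuity-corrected). That calculation returns 45 per arm, with power 80.6%. The plan gives no event count or power for PFS.

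**2. Scheduled evaluation days from start of therapy.** Regimen A: 21 × cycle. Regimen B: 7 + 21 × cycle.

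| End of cycle | 2 | 4 | 6 | 10 | 14 | 17 |
|---|---|---|---|---|---|---|
| Regimen A | 42 | 84 | 126 | 210 | 294 | 357 |
| Regimen B | 49 | 91 | 133 | 217 | 301 | 364 |

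The gap is 7 days throughout: 7/42 = 17% at the first evaluation and 7/357 = 2% at the last. Only the first three columns apply from Amendment 4. A tumour that progresses silently on day 30 is dated day 42 on A and day 49 on B.

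**3. What does not move.** Baseline imaging, unscheduled imaging at relapse or progression, and deaths are not tied to the cycle count. OS is therefore unaffected. Response is counted by cycle (best response by the end of 6 cycles), so this dating problem does not reach it.

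**4. Size under no true difference.** These inputs are assumptions, not protocol figures: exponential PFS with a median of 6 to 12 months, 1,000 days of follow-up, start uniform over 0-10 days after randomisation, scans 0-6 days early. There are 45 per arm and 4,000 simulated trials per case. The table gives rejection in favour of B by a one-sided 5% log-rank; the lower figure of each range belongs to the 12-month median and the higher to the 6-month median, except in the first and fifth rows.

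| Scenario | Rejection |
|---|---|
| No offset | 5.0-5.1% |
| 6-cycle schedule, later progression dated when it occurs | 5.7-6.9% |
| Same, with random cycle delays | 5.4-6.3% |
| 6-cycle schedule, later progression found only at the Section 7.1 visits | 6.1-7.1% |
| 6-cycle schedule, 30% of progressions found clinically | 5.3-5.4% |
| 17-cycle schedule, all patients assumed to reach Cycle 17 | 6.2-8.5% |
| Same, with random cycle delays | 5.6-7.7% |
| All later progression also found on shifted 91-day scans (not in the protocol) | 7.9-11.5% |

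The simulation standard error near 6% is √(0.06 × 0.94 / 4,000) = 0.4 percentage points, so the smallest excesses are barely distinguishable from 5%.

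On the hazard-ratio scale, with similar windows and medians of 6 to 18 months, the null HR (B v A) is 0.95-0.99 on the pre-Amendment 4 schedule and 0.98-1.00 from Amendment 4. From Amendment 4 only about 40% (6-month median) down to 21% (18-month median) of PFS events are seen on shifted evaluations.

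**5. After alignment.** Grouping progressions by scheduled evaluation returns the one-sided 5% test to about 4-5%. It is slightly conservative because B's first interval is a week longer. With a 6-month median (6 × 30.4375 = 182.6 days), the share progressing by day 42 is 1 − 0.5^(42/182.6) = 14.7%, and by day 49 it is 1 − 0.5^(49/182.6) = 17.0%. The common Cycle 2 time therefore takes in about 2 percentage points more events on B.

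**The case against.** The best case against acting is that the effect is minor. From Amendment 4 most PFS events fall after the last shifted evaluation, and the start and scan windows and cycle delays dilute the gap further. The choice of regimen rests on response alone (Section 9.3.4), as does interim monitoring (Section 9.3.3). Grouping by cycle also leaves events after Cycle 6, deaths and unscheduled progressions without a natural group. All of this stands. It limits the size, keeps the raw-date log-rank in place, and means the remedy needs explicit rules for those events.

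A reader might also infer more than the documents support:

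- *That every scan and every progression date moves by a week.* Section 15.1 includes imaging at relapse or progression, which is not tied to cycles, and PFS deaths need no scan.
- *That false-positive rates reach 8-11% or more.* That requires regular post-therapy scans carrying the same offset, which Section 7.1 does not schedule.
- *That the test runs at the trial's one-sided 20% level.* Section 9.3.1.1 assigns that level to response; none is assigned to PFS.

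What the objection does not remove is the direction. None of the shared windows offsets the gap. The extra 5-day eflornithine run-in after a delay of more than 7 days (Section 5.0) can only widen it, and is not in the figures above.

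**Conclusion.** The concern holds in a limited form. The 7-day offset on scheduled on-treatment and end-of-therapy evaluations follows directly from Sections 4.1, 4.6.1 and 15.1. The plan has no calendar-aligned schedule, dating rule, interval-censored analysis or sensitivity analysis to deal with it. The resulting tilt toward Regimen B is small: about 5.5-7% rejection against a nominal one-sided 5% on the 6-cycle schedule, and 6-8.5% on the 17-cycle schedule.

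Those figures rest on exponential PFS, an assumed median of 6 to 12 months, an assumed test level, and post-therapy progression being dated close to when it occurs. The documents give no median PFS for this regimen; their only related figure is 13.3 months for a different DFMO combination (Section 2.4). At longer medians the tilt is close to nil from Amendment 4. It is clearest in the pre-Amendment 4 cohort with early progression. The point does not threaten the primary conclusion. It bears on how far a modest PFS advantage for Regimen B may be cited in support of that conclusion.

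**What to change.** In Section 9.3.4, keep the raw-date Kaplan-Meier curves and log-rank, and add one pre-specified PFS comparison, overall and in the pre- and post-Amendment 4 cohorts:

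- Assign progressions found at a scheduled evaluation the nominal time of that evaluation, common to both regimens (end of Cycle 2, 4 and 6, and each later scheduled evaluation for pre-Amendment 4 patients). An interval-censored log-rank is an acceptable alternative.
- Let deaths, unscheduled progressions and events after the last scheduled evaluation keep their actual dates.
- State that a PFS advantage for Regimen B will be read as supportive only if it holds in this aligned analysis.

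The cost is a little more analysis work and, with grouped times, a slightly conservative test. On-treatment evaluations are already recorded by cycle, so the grouped version needs no new visits, scans or change to treatment.

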9.3.3 Monitoring for Futility or Efficacy of Regimen B

Monitoring for futility or efficacy of the DFMO arm will be performed. There would be cause to stop the trial early if the response rate on Regimen B appears to be insufficiently efficacious or superior to Regimen A. The response rates will be monitored after 2 cycles to decrease the amount of time the study must be closed for interim analysis. ANBL1221 data showed that most patients that responded on

the I/T/DIN arm did so early, with 16 of the 22 patients with confirmed responses demonstrating partial response or better after the first 2 cycles. With Amendment 4, the interim analysis will be done using overall response, or if overall response was coded as Not Done due to a missing component of the disease evaluation, the response at soft tissue and bone sites will be used as the overall response at the end of Cycle 2.

Futility monitoring will be performed per Ellenberg and Eisenberger (1985):⁶⁹ if at half the sample size the observed response rate after 2 cycles for Regimen B is less than that for Regimen A, accrual will be halted and the DSMC will consider permanently stopping accrual. Due to the potential for a drug supply issue, the futility analysis will be performed sooner, after accrual of 40 patients rather than at half the sample size of 45 patients. The futility rule will be executed once, using data from the first 40 eligible patients enrolled. This two-stage rule has been shown to lead to a reduction in the expected sample size if Regimen B is ineffective, with minimal loss in power.⁷⁰

A one-sided O'Brien-Fleming group-sequential boundary will be used to monitor for efficacy of Regimen B if the sample size is increased to 148 eligible patients. Interim monitoring will be performed at 50% of the expected information (N=74, 37 eligible patients per regimen), and 100% information. The critical p-values (upper boundary z-score) for the interim looks (maintaining an overall significance level of 20%) are 0.0699 (1.4763) at the first look, with the final analysis performed at a significance level of 0.1803 (0.9141).

If the futility and efficacy monitoring rules are not triggered, accrual will continue as planned, and the one-sided continuity-corrected test of proportions with pooled variance will be applied.

